6.2 COHORT 2: STUDY PROCEDURES

6.2.1 BASELINE PERIOD (STUDY DAY -42 TO STUDY DAY -1)

The Baseline Period of the study encompasses the screening activities that will occur on Study Day -42 as well as the observation period where subjects will be assessed for baseline seizure activity based on recordings of daily seizure activity entered into a diary.

6.2.2 SCREENING, CLINIC VISIT 1 (STUDY DAY -42 AND STUDY DAY -41)

Screening is the predetermined series of procedures with which each investigator selects an appropriate and representative sample of subjects for enrollment into the study. Select screening data will be documented in the IVR/IWR and eCRF.

Written informed parental or guardian consent and assent of minors (if the subject is capable of providing assent) must be obtained before a subject can start any of the screening procedures. The procedure(s) for obtaining written informed consent and assent of minor (if the subject is capable of providing assent) are described in [Section 11.2](#).

The Screening visit will occur on Study Day -42; however, the procedures may be split over 2 consecutive days (eg, Study Day -43 and Study Day -42, or Study Day -42 and Study Day -41). Splitting the visit procedures across 2 nonsequential days requires the approval of the Medical Monitor. The following procedures will be performed for all subjects before the start of seizure activity observation:

- Obtain written informed consent for the study
- Obtain written informed consent from parent/caregiver to collect EQ-5D-5L ratings of parent/caregiver symptoms and quality of life
- Review inclusion and exclusion criteria
- Record demographic information
- Record medical, neurological, and epilepsy history
- Record current epilepsy status (number/type/duration seizures per month)
- Collect past 6 months (or available duration) of parent/caregiver seizure diary data if available (screen shots of cell phones are acceptable, as are photocopies of paper diaries or print outs) and place in source file
- Administer healthcare utilization questions
- Administer Dravet syndrome outcomes measures
- Record prior medications
- Complete physical examination, including height, weight, and calculation of BMI
- Complete neurological examination
- 12-lead ECG
- Doppler ECHO (this may be obtained any time between Day -42 and Day -21)
- Vital signs (blood pressure, heart rate, temperature, and respiratory rate)
- Urine pregnancy test for females of child-bearing potential
- Laboratory evaluation (serum chemistry, hematology, urinalysis, etc)
- Urine THC panel
- Whole blood CBD
- Obtain blood sample for epilepsy genotype panel (one blood sample drawn between screening and Visit 10)

- Obtain buccal swab for CYP2D6 genotype/phenotype
- C-SSRS Children's Baseline/Screening Assessment ([Appendix 2](#))
- Instruct parent/caregiver on use of diary
- Dispense diary (after above procedures have been concluded)
- Record AEs
- Record AESIs

Only eligible subjects as specified by the inclusion and exclusion criteria with an independently confirmed diagnosis of Dravet syndrome by the Epilepsy Study Consortium will be enrolled into the study.

After enrollment into the study, each subject will be issued a “Subject Card” containing information about the subject’s participation in the study. The subject or parent/caregiver will be advised to retain this card on his person for the entire duration of the study so that the investigator or the Sponsor can be contacted in case of emergency.

In certain circumstances the Sponsor may allow subjects who did not meet all inclusion/exclusion criteria at the time of the Screening Visit to have the screening period extended, or to be rescreened for eligibility. In all cases the investigator should consult with the Medical Monitor. Decisions whether to permit rescreening resides solely with the Sponsor.

The decision whether to permit extended screening or rescreening can be influenced by many factors individual to that subject case. Some general principles apply:

1. If baseline seizure screening is extended or the subject is discontinued and then rescreened, the screening period for establishing the baseline seizure frequency will be the immediate 6 weeks before the randomization visit.
2. Subjects who are found to be on a prohibited medication at the screening visit may be weaned off of that medication provided:
 - a. Decisions to withdraw a disallowed concomitant medication must be made with the agreement of the prescribing physician.
 - b. If the medication has antiepileptic properties, a wash-out of at least 5 half-lives must be completed before collection of baseline seizure data.
 - c. If a decision has been made to wean off of a medication without antiepileptic properties and the wash-out period (at least 5 half-lives) is expected to be shorter than 5 weeks, then the subject may remain in screening and chart seizures using the seizure diary.

6.2.3 PHONE VISIT 2 (STUDY DAY -21)

Site personnel will contact the subject via telephone on Study Day -21 and record the following:

- AEs
- AESI
- Concomitant medications

In addition, site personnel will review the diary entries with the parent/caregiver.

6.2.4 CLINIC VISIT 3 (STUDY DAY -1): RANDOMIZATION

This period is intended to ensure that subjects meet the study entry criteria and confirm they have experienced ≥ 6 convulsive seizures during the 6-week Baseline Period, with at least 2 seizures in each 3-week half of the Baseline Period. Subjects must have at least 42 days of prospective diary data at Visit 3. Subjects will report to the clinic in the morning on Study Day -1 to allow for plasma sample collection for AED PK evaluation prior to the morning dose of these medications. Subjects should not take their morning dose(s) of AED medication prior to reporting to the clinic.

The following procedures will be performed on Study Day -1:

- Review inclusion and exclusion criteria
- Review current seizure activity (number/type/duration) from diary since previous visit and calculate the number of convulsive seizures during the first 3 weeks, the second 3 weeks, and over the full 6-weeks of the observation period.
- Record prior medications since previous visit
- Complete physical examination, including height and weight, and calculation of BMI
- Abbreviated neurological examination
- Vital signs (blood pressure, heart rate, temperature, and respiratory rate)
- 12-lead ECG
- Urine pregnancy test for females of child-bearing potential
- Laboratory evaluation (serum chemistry, and hematology, and urinalysis)
- Collect plasma sample for background AED PK evaluation prior to the morning dose of study medication(s)
- Urine THC panel
- Whole blood CBD
- Tanner Staging for subjects > 7 years of age ([Appendix 5](#))
- Collect and review diary with parent/caregiver
- Dispense diary
- C-SSRS Children's Since Last Visit Assessment ([Appendix 2](#))
- Healthcare utilization questions
- PedsQL Generic Core Scale ([Appendix 6](#))
- BRIEF ([Appendix 3](#))

- QOLCE ([Appendix 4](#))
- Parent/Caregiver QoL using the EQ-5D-5L scale ([Appendix 7](#))
- PedsQL Family Impact Module ([Appendix 6](#))
- Karolinska Sleepiness Scale
- Record AEs
- Record AESI
- When eligibility for the Titration Period is confirmed, randomize (blinded) subject to treatment assignment (ZX008 or placebo)
- Dispense study medication (If administration of the first dose of study medication occurs in the clinic, the next dose should be at least 8 hours later or the following morning. The dose on the following morning will count as Study Day 1.)

6.2.5 TITRATION AND MAINTENANCE PERIODS

6.2.5.1 Titration Period: Day 1

Subjects will take their first dose of study medication in the morning of Study Day 1. Study Day 1 is considered the first day of dosing, even for the subjects that received an in-clinic dose on Study Day -1.

6.2.5.2 Phone or Clinic Visit 4 (Titration Period: Day 8)

Site personnel will contact the subject via telephone or the subject can be reviewed in the clinic on Titration Period Day 8 and record the following:

- AEs
- AESI
- Concomitant medications

In addition, site personnel will review study medication dosing procedure and the diary entries with the parent/caregiver.

6.2.5.3 Clinic Visit 5 (Titration Period: Day 15)

Subjects will report to the clinic in the morning on Titration Period Day 15. The following procedures will be performed:

- Review current seizure activity (number/type/duration) from diary since previous visit
- Record concomitant medications
- Abbreviated physical examination, including height and weight, and calculation of BMI
- Abbreviated neurological examination
- Vital signs (blood pressure, heart rate, temperature, and respiratory rate)

- Collect and review diary with parent/caregiver
- Dispense diary
- CGI-I (assessed by parent/caregiver)
- CGI-I (assessed by investigator)
- Healthcare resource utilization questions
- Record AEs
- Record AESI
- Collect used, partially used and unused study medication; perform drug accountability and review with parent/caregiver
- Dispense study medication

6.2.5.4 Clinic Visit 6 (Maintenance Period: Day 22)

Subjects will report to the clinic in the morning on Maintenance Period Day 22. Subjects should not take their morning dose(s) of AED medication prior to reporting to the clinic. The following procedures will be performed:

- Review current seizure activity (number/type/duration) from diary since previous visit
- Record concomitant medications
- Abbreviated physical examination, including height and weight, and calculation of BMI
- Abbreviated neurological examination
- Vital signs (blood pressure, heart rate, temperature, and respiratory rate)
- Urine pregnancy test for females of child-bearing potential
- Laboratory evaluation (serum chemistry and hematology, and urinalysis)
- Urine THC panel
- Whole blood CBD
- Collect plasma sample for background AED PK evaluation prior to the morning dose of study medication(s)
- Collect and review diary with parent/caregiver
- Administer sleep quality and mealtime behavior questions
- Administer Karolinska Sleepiness Scale ([Appendix 8](#))
- Dispense diary
- C-SSRS Children's Since Last Visit Assessment ([Appendix 2](#))
- CGI-I (assessed by parent/caregiver)
- CGI-I (assessed by investigator)
- Record AEs
- Record AESI
- Collect used, partially used and unused study medication; perform drug accountability and review with parent/caregiver
- Dispense study medication

6.2.5.5 Phone Visit 7 (Maintenance Period: Day 36)

Site personnel will contact the subject via telephone on Maintenance Period Day 36 and record the following:

- AEs
- AESI
- Concomitant medications
- Healthcare utilization questions

In addition, site personnel will review study medication dosing procedure and the diary entries with the parent/caregiver.

6.2.5.6 Clinic Visit 8 (Maintenance Period: Day 50)

Subjects will report to the clinic in the morning on Maintenance Period Day 50. Subjects should not take their morning dose(s) of study medication and AED medication prior to reporting to the clinic. The following procedures will be performed:

- Review current seizure activity (number/type/duration) from diary since previous visit
- Record concomitant medications
- Abbreviated physical examination, including height and weight, and calculation of BMI
(Note: if the subject's weight is $\pm 25\%$ of the weight at Day -1, the IMP dose will be recalculated)
- Vital signs (blood pressure, heart rate, temperature, and respiratory rate)
- 12-lead ECG
- Doppler ECHO (this must be obtained any time between Day 40 and Day 54)
- Urine pregnancy test for females of child-bearing potential
- Laboratory evaluation (serum chemistry and hematology, and urinalysis)
- Urine THC panel
- Whole blood CBD
- Collect plasma sample for background AED PK evaluation prior to the morning dose of study medication(s)
- Collect and review diary with parent/caregiver
- Dispense diary
- C-SSRS Children's Since Last Visit Assessment ([Appendix 2](#))
- PedsQL Generic Core Scale ([Appendix 6](#))
- BRIEF ([Appendix 3](#))
- QOLCE ([Appendix 4](#))
- PedsQL Family Impact Module ([Appendix 6](#))
- CGI-I (assessed by parent/caregiver)

- CGI-I (assessed by investigator)
- Administer sleep quality and mealtime behavior questions
- Karolinska Sleepiness Scale ([Appendix 8](#))
- Record AEs
- Record AESI
- Collect used, partially used and unused study medication; perform drug accountability and review with parent/caregiver
- Dispense study medication

6.2.5.7 Phone Visit 9 (Maintenance Period: Day 64)

Site personnel will contact the subject via telephone on Maintenance Period Day 64 and record the following:

- AEs
- AESI
- Concomitant medications
- Healthcare utilization questions

In addition, site personnel will review study medication dosing procedure and the diary entries with the parent/caregiver.

6.2.5.8 Clinic Visit 10 (Maintenance Period Day: 78)

Subjects will report to the clinic on Maintenance Period Day 78. The following procedures will be performed:

- Review current seizure activity (number/type/duration) from diary since previous visit
- Record concomitant medications
- Abbreviated physical examination, including height and weight, and calculation of BMI
- Vital signs (blood pressure, heart rate, temperature, and respiratory rate)
- Urine pregnancy test for females of child-bearing potential
- Laboratory evaluation (serum chemistry and hematology, and urinalysis)
- Urine THC panel
- Whole blood CBD
- Collect and review diary with parent/caregiver
- Dispense diary
- C-SSRS Children's Since Last Visit Assessment ([Appendix 2](#))
- CGI-I (assessed by parent/caregiver)
- CGI-I (assessed by investigator)
- Administer sleep quality and mealtime behavior questions

- Karolinska Sleepiness Scale ([Appendix 8](#))
- Record AEs
- Record AESI
- Collect used, partially used and unused study medication; perform drug accountability and review with parent/caregiver
- Dispense study medication

At Clinic Visit 10, compliant subjects who have tolerated IMP should be presented with the ICF for the open-label extension trial. Informed consent for the open-label extension trial must be signed at Visit 12 or earlier in order to enter the open-label extension trial.

6.2.5.9 Phone Visit 11 (Maintenance Period: Day 92)

Site personnel will contact the subject via telephone on Maintenance Period Day 92 and record the following:

- AEs
- AESI
- Concomitant Medications
- Healthcare utilization questions

In addition, site personnel will review study medication dosing procedure and the diary\entries with the parent/caregiver.

6.2.5.10 Clinic Visit 12 (End of Study/Early Termination: Day 106)

The End-of-Study participation for an individual subject occurs after he/she has received IMP for 12 weeks in the Maintenance Period. At the End-of-Study visit, the subject may enroll into the separate extension trial if they have completed 12 weeks of treatment in the Maintenance Period. Other circumstances for participation in the extension trial are described in [Section 4.8](#).

The End-of-Study visit may also occur if the subject withdraws participation from the study or the Sponsor terminates the study. If the subject withdraws participation from the study, they may on a case-by-case basis, be eligible for entrance into the separate open-label extension trial after consideration of the circumstances of the early termination and the potential benefit-risk of continued participation in a ZX008 trial. The decision whether to permit open-label extension trial participation resides solely with the Sponsor, who may consult with the site investigator. If the Sponsor terminates the study early, the subject may or may not be offered enrollment into the open-label extension, depending on the reason for termination.

Subjects will visit the clinic for the End-of-Study visit if one the following events occur:

- The subject withdraws or is withdrawn from participation in the study.
- The Sponsor terminates the study.
- The subject completes all study related visits and procedures.

The following procedures will be performed:

- Review current seizure activity (number/type/duration) from diary since previous visit
- Record concomitant medications
- Complete physical examination, including height and weight, and calculation of BMI
- Complete neurological examination
- Vital signs (blood pressure, heart rate, temperature, and respiratory rate)
- 12-lead ECG
- Doppler ECHO (must be performed any time between Day 90 and Visit 13; if subject terminates early from the study, the ECHO should be scheduled as soon as practical. If the Day 43 ECHO was completed \leq 30 days prior to early termination, the Visit 12 ECHO will not be performed provided the parent/guardian agrees to bring the subject to the clinic for the cardiac follow-up visit (see [Table 10](#)).
- Urine pregnancy test for females of child-bearing potential
- Laboratory evaluation (serum chemistry and hematology, and urinalysis)
- Urine THC panel
- Whole blood CBD
- Collect plasma sample for background AED PK evaluation prior to the morning dose of study medication(s)
- Tanner Staging for subjects $>$ 7 years of age ([Appendix 5](#))
- Collect and review diary with parent/caregiver
- Dispense diary
- C-SSRS Children's Since Last Visit Assessment ([Appendix 2](#))
- CGI-I (assessed by parent/caregiver)
- CGI-I (assessed by investigator)
- Healthcare utilization questions
- Sleep quality and mealtime behavior questions
- Karolinska Sleepiness Scale ([Appendix 8](#))
- PedsQL Generic Core Scale ([Appendix 6](#))
- BRIEF ([Appendix 3](#))
- QOLCE ([Appendix 4](#))
- Parent/Caregiver QoL using the EQ-5D-5L scale ([Appendix 7](#))
- PedsQL Family Impact Module ([Appendix 6](#))
- Record AEs
- Record AESI

- Collect used, partially used and unused study medication; perform drug accountability and review with parent/caregiver
- Dispense study medication for taper for subjects not enrolling in the open-label extension trial
- Dispense study medication for transition for subjects enrolling in the open-label extension trial

Informed consent for the open-label extension trial must be signed at Visit 12 (if not signed earlier) in order to enter the open-label extension trial.

6.2.5.11 Follow-up Visit (Clinic Visit 13; Day 120)

Subjects will report to the clinic in the morning of Visit 13. Subjects should not take their last dose of study medication or morning dose of antiepileptic medication prior to reporting to the clinic so that 4 blood samples can be obtained for steady-state PK.

For subjects entering the open-label extension trial, the subject will visit the clinic on Visit 13 (Day 120). The following will be recorded/Performed and the subject will immediately be enrolled in that separate study:

- Review current seizure activity (number/type/duration) from diary since previous visit
- AEs
- AESI
- Concomitant medications
- Collect used, partially used and unused study medication; perform drug accountability and review with parent/caregiver
- Collect plasma sample for ZX008 PK evaluation prior to the morning dose of study (last dose of Protocol 1504 study medication) and their usual AED medication(s)
- Collect additional plasma samples for ZX008 PK evaluation at 1, 2, and 4-6 hours post-dose

If the subject does not enter the open-label extension trial (or discontinues from the study early), the subject will visit the clinic on Visit 13 (Day 120) (or 14 days after the day of discontinuation). The following will be recorded/Performed:

- Review current seizure activity (number/type/duration) from diary since previous visit
- AEs
- AESI
- Concomitant medications
- Collect used, partially used and unused study medication; perform drug accountability and review with parent/caregiver

6.2.6 CARDIAC FOLLOW-UP VISIT (COHORT 1: CLINIC VISITS 18, 19/COHORT 2: CLINIC VISIT 14; 3-6 MONTHS AFTER LAST DOSE OF STUDY MEDICATION)

If the subject completes the study but does not enter the open-label extension trial or discontinues from the study early, the subject will return to the clinic for follow-up cardiac testing (ECHO, ECG, and in some cases physical examination). The timing and frequency of exams are presented in [Table 10](#). Subjects on blinded medication who are found to have been on placebo are not required to participate in follow-up testing once the blind is broken at the end of the study. As the ECHO and ECG will be administered in a separate clinic from the pediatric neurology clinic, an asymptomatic subject receiving a second follow-up ECHO and ECG does not require a physical examination.

Subjects with positive findings on ECHO, ECG and/or physical examination should continue to be followed until the finding is resolved or stable and unlikely to change, with reports submitted as AESI to the ZX008 safety database.

Table 10. Schedule of Post-Treatment Cardiac Follow-up

Parameter	Duration of Blinded ^a or Fenfluramine Treatment				Have had any cardiac sign or symptom regardless of the time on study drug ^b
	Less than 2 weeks Cumulative	2 to 4 weeks	> 4 and < 13 weeks	> 13 weeks	
ECHO	No	Yes, 3 months post-treatment	Yes, 3 months post-treatment	Yes, 3-6 months post-treatment	Yes, 3 and 6 months post-treatment, and until resolved, or stable and unlikely to change
ECG	No	Yes, 3 months post-treatment	Yes, 3 months post-treatment	Yes, 3-6 months post-treatment	Yes, 3 and 6 months post-treatment and until resolved, or stable and unlikely to change
Physical examination	No	Yes, 3 months post-treatment	Yes, 3 months post-treatment	Yes, 3 months post treatment only	Yes, 3 and 6 months post-treatment, and until resolved, or stable and unlikely to change

ECG = electrocardiogram; ECHO = echocardiogram; IPCAB = International Pediatric Cardiology Advisory Board

^a If blind is broken at the end of the study and a subject revealed to have taken only placebo, no further testing is required.

^b Positive sign or symptom includes any development of valve thickening or regurgitation “trace” or greater in mitral, aortic, mild or greater in pulmonary, tricuspid), or sign or symptom indicative of potential pulmonary hypertension as adjudicated by the IPCAB.

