activity entered into a diary. Upon completion of the Baseline Period, subjects who qualify for the study will be randomized (1:1) in a double-blind manner to receive ZX008 (at a dose of 0.5 mg/kg/day; maximum dose 20 mg/day) or placebo. Randomization will be stratified by age group (< 6 years, ≥ 6 years) to ensure balance across treatment arms, and at least 40% of subjects will be in each age group. Titration will occur in 3 steps starting with a 0.2 mg/kg/day dose of ZX008 (or placebo equivalent) on Study Days 1-7, increased to a dose of 0.4 mg/kg/day on Study Days 8-14, and then increased to a dose of 0.5 mg/kg/day on Study Days 15-21. The duration of the Titration Period is 21 days, and the maximum daily dose at any point is 20 mg/day. Following titration, subjects will continue treatment with the assigned dose of ZX008 0.5 mg/kg/day or placebo over a 12-week Maintenance Period. Total treatment time from the beginning of the Titration Period through the end of the Maintenance Period is a maximum of 15 weeks. At the end of the Maintenance Period (or early discontinuation), all subjects will enter either a taper or transition period based on whether they exit the study or are enrolled in the separate long-term open-label extension trial, respectively. PK samples will be collected during the Follow-Up visit for subjects who will be entering the open-label extension. A follow-up ECG and ECHO will be performed 3-6 months after study drug discontinuation for early termination, or for those subjects who complete the study but do not enter the open-label extension trial Cohort 2 only).

Parents/caregivers of subjects in Cohort 2 will use a diary daily to record the number/type of seizures, dosing, and use of rescue medication. A schedule of assessments is provided in [Table 2](#).

External Individuals and Committees: The ZX008 clinical program will employ an Independent Data and Safety Monitoring Committee (IDSMC) that will be responsible for safety oversight. A separate International Pediatric Cardiology Advisory Board (IP CAB) will monitor the cardiac safety of the ZX008 clinical trials. ECGs and Doppler ECHOs will be centrally read (Biomedical Systems, Inc.) and interpreted under blinded conditions using pre-specified criteria, and if necessary, with review by the IP CAB. The IDSMC will be informed of the dose selected for Cohort 2.

Number of Subjects:

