Pharmacokinetics: Blood samples for PK assessment of fenfluramine and its metabolite (norfenfluramine), STP, CLB and its metabolite (n-desmethylclobazam [N-CLB]), and valproic acid (VPA) will be obtained from subjects according to the schedule in [Table 1](#) (a total of 6 samples per subject).

Safety: PK portion of the study: AEs, physical examination, vital signs, ECG, clinical laboratory parameters (standard hematology, clinical chemistry, urinalysis). Transition period: AEs, laboratory safety parameters (hematology, chemistry, urinalysis), vital signs (blood pressure, heart rate, temperature, and respiratory rate), physical examination, neurological examination, 12-lead ECGs,

Doppler ECHOs, and body weight. Cognitive Function will be assessed using the cognition domain score on the QOLCE and age-appropriate versions of the BRIEF.

Cohort 2

Efficacy:

- Number of seizures by type
- Convulsive seizure-free interval
- QOLCE to measure subject's quality of life
- PedsQL Generic Core Scale to measure changes in HRQOL of the subject
- HRQOL of parent/caregiver using the EQ-5D-5L scale
- Impact of condition on parent/caregiver using PedsQL Family Impact Module
- Duration of prolonged seizures (seizure type that, during baseline, had duration > 2 minutes)
- Number of episodes of SE
- Number of instances of rescue medication use and number of doses
- Number of inpatient hospital admissions due to seizures
- CGI-I score assessed by the principal investigator
- CGI-I score assessed by the patient/caregiver

Safety: AEs, laboratory safety parameters (hematology, chemistry, urinalysis), vital signs (blood pressure, heart rate, temperature, and respiratory rate), physical examination, neurological examination, 12-lead ECGs, Doppler ECHOs, and body weight. Cognitive Function will be assessed using the cognition domain score on the QOLCE and age-appropriate versions of the BRIEF.

Pharmacokinetics: Four sequential blood samples will be collected during Visit 13 for steady-state PK. Fenfluramine /nor-fenfluramine concentration-time data from subjects enrolled in Cohorts 1 and 2 will be used to model PK of ZX008 in single and multiple dose regimens.

Exploratory:

- Health and social care resource use including GP visits, speech and language, occupational and physical therapy, in addition to acute hospital and institutional length of stay, loss of work, etc.
- Change in sleep quality assessed by the patient/caregiver

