- d: The Visit 8 ECHO must be performed any time between Study Day 40 and Study Day 54. The Visit 12 ECHO must be performed any time between Study Day 90 and Study Day 113; if a subject discontinues early from the study, the ECHO should be scheduled as soon as practical. If the Study Day 43 ECHO was completed \leq 30 days prior to early termination, the Visit 12 ECHO will not be performed provided the parent/guardian agrees to bring the subject to the clinic for the cardiac follow-up visit.
- e: Females of child-bearing potential
- f: Plasma sample for PK assessment will be conducted prior to the dose at the Follow-up visit and 1, 2, and 4-6 hours after dose administration for Subjects continuing into the open-label extension trial.
- g: Plasma sample for assessment of background AED(s) will be conducted prior to the dose of AED(s) at Visits 3, 6, 8 and 12.
- h: Study drug/diary dispensed for the transition for subjects entering the open-label extension trial and for tapering for subjects exiting the study.
- i: Site personnel will review study medication dosing procedure (titration) with parent/caregiver.
- j: Study drug administration begins in the morning of Study Day 1.
- k: Only adverse events related to cardiac safety will be collected at this visit.
- l: Mandatory one time collection any time during or after screening and before Visit 10.

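### Protocol 6.2.5.11 asks subjects, without restriction, to hold the morning antiepileptic dose before Visit 13, although the PK samples that justify the hold are planned only for extension entrants

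*Protocol*

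**What the plan says.** The opening paragraph of Protocol 6.2.5.11 states: "Subjects should not take their last dose of study medication or morning dose of antiepileptic medication prior to reporting to the clinic". The sentence then gives its purpose: "so that 4 blood samples can be obtained for steady-state PK". Only after that does the section divide into two procedure lists.

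- **Extension entrants.** A ZX008 PK sample is taken before dosing, and further samples at 1, 2 and 4-6 hours after it. The first is timed "prior to the morning dose of study (last dose of Protocol 1504 study medication) and their usual AED medication(s").
- **Subjects not entering the extension, and early discontinuers.** The list covers diary review, AEs, AESIs, concomitant medications and drug accountability. It contains no blood sample.

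Other texts on who is sampled at Visit 13:

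- Synopsis, Methodology: "PK samples will be collected during the Follow-Up visit for subjects who will be entering the open-label extension".
- Table 2 footnote f, and the same footnote in SAP Table 5: samples before the dose and "1, 2, and 4-6 hours after dose administration for Subjects continuing into the open-label extension trial".
- Synopsis, Criteria for Evaluation: "Four sequential blood samples will be collected during Visit 13 for steady-state PK", with no restriction.
- Section 7.4: four samples per subject, again without saying which subjects. The only analytes named for Cohort 2 are fenfluramine and norfenfluramine.

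On background AED levels, Table 2 footnote g says: "Plasma sample for assessment of background AED(s) will be conducted prior to the dose of AED(s) at Visits 3, 6, 8 and 12". Visit 13 is not among them.

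**The concern.** The group told to hold doses is wider than the group sampled. A site that follows the opening paragraph as written would ask a child who is leaving the programme to arrive without the morning AEDs, and would then draw no PK or AED sample.

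The children concerned have refractory convulsive seizures: inclusion criterion 5 requires at least 4 per 4-week period. Some would be early discontinuers, and worsening seizures is one of the discontinuation reasons in Section 4.5. Section 5.7 asks that existing AED regimens be kept stable. What is at stake is a small, avoidable delay to background treatment, not the efficacy analysis.

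**Working it through.** This is mainly a comparison of texts, with two short arithmetic checks.

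**1. Is a PK or AED sample planned at Visit 13 beyond the entrants' ZX008 samples?** Protocol Table 12 gives the planned Cohort 2 blood volumes.

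- Visit 13 column: 4 × 2 mL ZX008 PK + 4 × 0.5 mL flush = 10 mL. The table states 10 mL.
- AED row: 4 × 2 mL (Days -1, 22, 50, 106) = 8 mL. The table states 8 mL. Those days are Visits 3, 6, 8 and 12, so nothing is left for Visit 13.
- Total: 20.7 + 17.7 + 17.7 + 17.7 + 15.7 + 17.7 + 10 = 117.2 mL. The table states 117.2 mL.

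A 2 mL AED sample at Visit 13 would make these 12, 10 and 119.2 mL, which do not match. Table 12 therefore agrees with footnote g that no AED sample is planned there.

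**2. Do subjects not entering the extension have a study dose to hold?**

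- Section 3.3 puts the follow-up visit 14 days after completion or early termination.
- Table 6 puts the last taper dose on Day 8 after completion or early termination.
- Gap: 14 − 8 = 6 days. For completers: 106 + 8 = 114, and 120 − 114 = 6 days. Section 5.5.5 likewise gives no drug in the last 6 days of the taper.
- The 6 days are nominal. Table 9 allows ±4 days at Visit 13, so with the taper dates fixed the gap runs from 6 − 4 = 2 to 6 + 4 = 10 days. The taper is over in every case.

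**3. Side by side at Visit 13**

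| | Entering the extension | Not entering |
|---|---|---|
| Covered by the hold sentence as written | Yes | Yes |
| Study dose due that morning | Yes | No |
| ZX008 PK samples planned | 4 | 0 |
| Background AED samples planned | 0 | 0 |
| Stated purpose served by holding AEDs | Yes: the first PK sample precedes them | None |

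The mismatch is confined to the right-hand column.

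**The case against.** The strongest reply is that the sentence limits itself. It speaks of a last dose of study medication and of steady-state sampling, and neither exists for someone who finished the taper days earlier. It also leads straight into the entrant list, which repeats the pairing of study dose and usual AEDs. Section 7.4 can be read as a count per sampled subject, and 10.5.3 refers to those Cohort 2 patients who undergo PK sampling, which fits a subset. All of this stands as evidence of intent. It does not supply an exemption: the AED part of the instruction makes sense for anyone who takes AEDs, and two other unrestricted texts (7.4 and the synopsis evaluation section) could confirm a site in the wider reading.

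The reply that the consequence is slight also stands. The dose is delayed, not omitted, and the protocol states an AED hold at Visits 3, 6 and 8. At those visits, however, an AED sample is drawn.

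Three stronger readings are tempting, and the documents do not support them:

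- That the plan deliberately withholds AEDs from everyone. The text says subjects, not all subjects, and its purpose clause points to entrants.
- That having no AED sample at Visit 13 is itself a defect. For entrants the hold is justified without one, because the pre-dose ZX008 sample is to precede their AEDs.
- That every early discontinuer is a non-entrant. Sections 4.8 and 6.2.5.10 allow some into the extension case by case.

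Section 6.3 mentions a Visit 13 chemistry and hematology draw. That could not justify the hold either: no AED hold is stated for it, and it is neither a PK nor an AED sample.

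**Conclusion.** The inconsistency is real but minor. As written, the hold reaches subjects for whom no Visit 13 PK or AED sample is planned, and no text exempts them. The literal effect is one morning AED dose delayed until arrival for each attending subject who does not enter the extension. How many there would be, how long the delay would last and what seizure risk it carries are not given, so none is estimated here.

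No primary or key secondary endpoint is affected: they are measured over T + M, and Section 10.4.2 places Visit 13 in the Follow-up Period after it. One supplementary analysis might touch that day: the Maintenance-only repeat in SAP 6.3.1.1 borrows Transition data for subjects who never reached Maintenance, and SAP 6.1.6 ends Taper/Transition at Visit 13. At most that is one diary day per such subject.

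The conclusion assumes that the four texts restricting sampling to entrants govern over the two unrestricted ones. The lack of any steady state in subjects off drug supports that. If the unrestricted texts governed instead, the documents would still conflict and need alignment.

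**What to change.** 1. Move the hold sentence in 6.2.5.11 into the paragraph for subjects entering the open-label extension.
2. Add a sentence saying that subjects not entering the extension take their usual morning AEDs before Visit 13, and that early discontinuers who have been admitted to the extension follow the entrant instructions.
3. In 7.4 and in the Visit 13 sentence of the synopsis evaluation section, limit the four PK samples to subjects continuing into the extension.

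The cost is one sentence moved, one added and two phrases aligned. No planned PK data are lost, because every planned Visit 13 PK draw is in a subject entering the extension.
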